### **10.7.3 Sensitivity analyses**

Sensitivity analyses will be implemented to assess the robustness of results on primary endpoint versus assumptions used in the statistical model for the main estimator.

The following sensitivity analyses will be performed:

- Tipping-point analysis: based on the assumption that subjects on active treatment who discontinue from the study perform worse by some amount than subjects of the same group remaining in the study (Section 10.7.3.1).
- Copy reference approach: based on the assumption that subjects on active treatment with any missing data follow the distribution of the ones in the placebo group (Section 10.7.3.2).
- Complete cases analysis (Section 10.7.3.3);
- Main analysis on the PPS.
- Main analysis stratified by ADHD severity at baseline.

#### ***10.7.3.1 Tipping point sensitivity analysis***

For the imputation of missing data of AISRS, MI will be implemented assuming the MAR and imputing all missing data including missing data occurred/imputed after IEs as described in policy strategies 1 and 2. A delta-adjusted imputation method will be used applying progressive stress test to the MAR assumption of the main analysis. That is, a tipping-point analysis will be performed to see how severe departures from the MAR assumption should be to overturn the conclusions of the main analysis. It is assumed that study subjects from the MM-120 group with missing values would have, on average, their observed efficacy score worsened by some amount (delta) compared

with the efficacy score observed in study subjects of the same MM-120 group remaining in the study. A series of analysis models defined above with progressively increasing deltas ( $\delta = 0, 1, 2, 3, \dots$ ; from less conservative to more conservative, where a delta of zero,  $\delta(0)$ , corresponds to the reference) will be run until the model results to be not significant ( $p\text{-value} \geq 0.05$ ). The delta adjustment will only be applied to the multiple-imputed values (based on the MAR assumption) of the subjects in the MM-120 group. Same linear mixed effects model defined for the main analysis will be used.

The Tipping point analysis will be performed only in case the main analysis of the primary endpoint resulted significant.

#### **10.7.3.2 *Copy reference***

A reference-based MI approach will be adopted considering a Missing Not at Random (MNAR) mechanism for all missing data of all IE events described in policy strategies 1 and 2: imputation of values in the MM-120 group will be done using the non-missing values of the placebo group (this approach will be referred as “Copy Reference”). This approach does not assume benefits for MM-120 in case of discontinuation and limits a post-discontinuation clinical effect to that of placebo.

#### **10.7.3.3 *Complete cases***

The analysis of primary endpoint will be performed by fitting the MMRM on complete cases only (observed data) i.e., without implementing the MI and without the use of the “policy strategies”.

#### **10.7.3.4 *Sensitivity analysis on the PPS population.***

Main analysis defined in Section 10.7.2 will be performed on the PPS population.

#### **10.7.3.5 *Sensitivity analysis stratified by ADHD severity.***

Main analysis defined in Section 10.7.2 will be stratified by ADHD severity at baseline (see definition of subgroup populations in Section 9.3) and analysed on FAS.

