13.6.4. Sample size determination

Randomizing 26 subjects per arm, if the true efficacy of MM-120 reaches a standardized mean improvement over placebo of 0.60, the null hypothesis that active is not better than placebo will be rejected with a one-sided p-value < 0.10 with 80% power.

The minimum estimated standardized effect size resulting in a p-value < 0.10 is 0.38 while an estimated standardized effect size < 0.56 will result in a one-sided p-value < 0.025.

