## 2 TRIAL DESIGN, STUDY DOCUMENTS, DATABASE CODING

### 2.1 TRIAL DESIGN

#### 2.1.1 Trial design

This is a randomized, double-blind, placebo-controlled, Phase 2a study on the efficacy and safety of repeated low dose D-lysergic acid diethylamide (LSD) D-Tartrate (MM-120) in adult subjects aged  $\geq 18$  and  $\leq 65$  with attention-deficit/hyperactivity disorder (ADHD).

Eligible subjects that consent to participate will be randomized in a 1:1 allocation to placebo or MM-120.

There will be 2 arms:

- Arm 1-Placebo: a total of 26 subjects will receive a placebo identical in appearance to the IMP administered orally twice weekly for 6 weeks. Subjects and site staff will remain blinded to the treatment group.
- Arm 2-MM-120: a total of 26 subjects will receive 20  $\mu$ g of MM-120 twice weekly for 6 weeks. Subjects and site staff will remain blinded to the treatment group.

Potential study subjects who provide informed consent will have eligibility evaluated/confirmed at 2 visits: 1) Screening, and 2) Baseline. The screening visit occurs up to 4 weeks prior to Baseline. An assessment will be made to confirm or make the ADHD diagnosis with the Mini International Neuropsychiatric Interview (MINI). The subject must have an Adult Attention Deficit Investigator Symptom Rating Scale (AISRS) score of  $\geq 26$  and a Clinical Global Impression - Severity of Illness Scale (CGI-S) score of  $\geq 4$  at screening and must meet all other eligibility criteria:

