## 9.3 SUBGROUPS

Primary endpoint main analysis will be performed on the following subgroup populations:

**1. Severe ADHD:** Adult Attention Deficit Investigator Symptom Rating Scale (AISRS) score of  $\geq 38$  at baseline.

**2. Moderate ADHD:** Adult Attention Deficit Investigator Symptom Rating Scale (AISRS) score of  $< 38$  at baseline.

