### 10.7.1 Statistical model and hypotheses

The null hypothesis is that active MM-120 is not better than placebo; this will be rejected with a one-sided p-value < 0.10 with 80% power if the true efficacy of MM-120 reaches a standardized mean improvement over placebo of 0.60.

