#### **10.7.2.2 Analysis details**

Primary endpoint, change in AISRS score from baseline to Week 6, will be analyzed applying Rubin's rule to a multiple imputations procedure to appropriate contrasts based on Mixed Model for Repeated Measures (MMRM) analysis of covariance with the change in the AISRS score from baseline to Week 2 and Week 6 visits as dependent variable, and treatment group, visit, visit-by-treatment group interaction, baseline score of AISRS, sex and age as fixed effects. An unstructured variance-covariance matrix will be used to model within-subject errors. Satterthwaite's method will be used to approximate the degrees of freedom. If convergence problems arise (even just in one imputed dataset) the following order of matrices will be applied: Heterogeneous TOEP (TOEPH), Toeplitz (TOEP), Autoregressive(1) (AR(1)). The same variance-covariance matrix will be used in sensitivity analyses.

The imputation model include the longitudinal sequence of AISRS Scores, and the covariates used in the model as defined above. As a general approach, imputations are performed on observed values specifying a minimum and a maximum threshold (zero and 54 respectively) for AISRS. The change from baseline in AISRS Scores will not be imputed to avoid imputation of nonsensical values. For the imputation of missing data of AISRS, one thousand (1000) data sets will be generated, and the random seed number will be 200208. MI will be implemented following the steps below:

1. Imputation assuming a MAR (policy strategy 1).

MAR will be applied following the steps below:

- a)all assessments that took place after the IEs related to COVID-19 pandemic will be kept in the database;
- b)imputing all missing values already present in the data.

MI will be carried out based on fully conditional specification method (FCS, the details will be provided in the 'Programming standards and conventions' document). These datasets will be utilized in Step #2.

2. Imputation assuming MNAR (policy strategy 2).

MNAR will be applied following the steps below:

- a)assigning missing values to all assessments that took place after the IEs specified in policy strategy 2 above;
- b)imputing missing values assigned at step (a).

MNAR assumption based on copy reference approach (i.e. using the non-missing values of the placebo arm) will be used.

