### 13.1.16 Layout T16

Study MMED007 - Deliverables: <Deliverables>

Table <Number of table>

<Title>

Analysis set: <analysis set>

Severe ADHD (AISRS score at baseline  $\geq$  38) | Moderate ADHD (AISRS score at baseline  $<$  38)

Visit Treatment group	n	LS Mean	SE	95% CL	Difference to placebo				p-value*
					LSMean	SE	95% CL		
Change from Baseline to Week 6									
MM-120	xx	xx.x	xx.x	[xx.x, xx.x]	xx.x	xx.x	[xx.x, xx.x]	0.xxx	
Placebo	xx	xx.x	xx.x	[xx.x, xx.x]	-	-	-	-	

\*p-value is one-sided

\*\*MMRM=Mixed Model for Repeated Measures

Program: `program_name.sas`, Produced on yyyy-mm-dd hh:mm (CET),

Snapshot date: yyyy-mm-dd, Draft/final

Page x of x

Note for programmer:

-for "MMRMAISRS" dependent variable is AISRS Score (analysis performed on FAS);  
 -for "MMRMAR" dependent variable is AISRS Score, with MAR assumption (analysis performed on FAS); add Footnote: \*\*\* MAR= Missing At Random.  
 -for "MMRMNAR" dependent variable is AISRS Score, with MNAR assumption (analysis performed on FAS); add Footnote: \*\*\* MNAR= Missing Not At Random.  
 -for "MMRMCP" dependent variable is AISRS Score, completed cases (analysis performed on FAS)  
 -for "MMRMAISRS" dependent variable is AISRS Score (analysis performed on PPS)

Please use subgroups 'Severe ADHD (AISRS score at baseline  $\geq$  38) | Moderate ADHD (AISRS score at baseline  $<$  38)' in the sensitivity analysis of the MMRMAISRSSEV

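### The severity analysis prints a p-value in each stratum but no estimate of the difference between strata, so discordant p-values would say little about severity or robustness

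*SAP*

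**What the plan says.** - SAP 9.3 defines severe (baseline AISRS 38 or more) and moderate (below 38) ADHD and says: "Primary endpoint main analysis will be performed on the following subgroup populations".
- SAP 10.7.3.5 repeats this for the FAS: "Main analysis defined in Section 10.7.2 will be stratified by ADHD severity at baseline". SAP 10.7.3 lists it with the tipping-point, copy-reference, complete-case and per-protocol analyses, which are there to test how far the primary result depends on the model's assumptions.
- The model to be rerun (SAP 10.7.2.2) has these terms: "treatment group, visit, visit-by-treatment group interaction, baseline score of AISRS, sex and age as fixed effects". It has no severity term, and its only interaction is treatment by visit.
- Shell T16 tells the programmer to use the two severity subgroups "in the sensitivity analysis of the MMRMAISRSSEV". It shows n, LS means, difference to placebo, SE, 95% limits and a one-sided p-value, with no row comparing the two strata.
- Protocol 13.6.6 describes analyses within subpopulations as exploratory.

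Neither document plans a treatment-by-severity estimate, a difference between stratum effects or a criterion for consistency. Neither gives the expected share of subjects in each stratum.

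**The concern.** Splitting the trial by severity asks whether the effect of MM-120 depends on how ill the subject is at baseline. Only a comparison of the two stratum effects answers that. Two p-values do not, because each also reflects the size of its stratum.

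The label adds to the problem. The other analyses in SAP 10.7.3 vary the handling of missing data or the analysis set. This one varies the population, which is a subgroup question. Placed under a robustness heading, a table with one p-value below 0.10 and one above it invites one of two conclusions: that the drug works only in one severity group, or that the primary result is fragile. If discordant p-values are common under a perfectly constant effect, neither conclusion is warranted, and the planned table contains nothing that says so.

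**Working it through.** **Inputs**
- Test: one-sided 0.10 (SAP 10.7.1: "this will be rejected with a one-sided p-value < 0.10 with 80% power").
- True effect: "standardized mean improvement over placebo of 0.60" (SAP 10.7.1).
- Size: "Randomizing 26 subjects per arm" (protocol 13.6.4).
- Allocation: "Eligible subjects that consent to participate will be randomized in a 1:1 allocation to placebo or MM-120" (SAP 2.1.1). Severity is not named as a randomisation factor.
- Severity split: not given. I assume 13 per arm in each stratum and show uneven splits as well.

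**1. The plan's own figure.** Power = Φ(δ√(n/2) − z), with z = 1.2816 for one-sided 0.10. For n = 26 and δ = 0.60: 0.60 × √13 = 2.163, and Φ(2.163 − 1.2816) = 0.811. The noncentral t with 50 df gives 0.806. The stated 80% reproduces.

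**2. Power in one stratum.** For n = 13: 0.60 × √6.5 = 1.530, and Φ(1.530 − 1.2816) = 0.598. The noncentral t with 24 df gives 0.588. Call it 59%.

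**3. Agreement of the two p-values under a constant effect.** The strata contain different subjects, so the two tests are independent. With powers p1 and p2, the chance that exactly one is significant is p1(1 − p2) + p2(1 − p1).
- Exactly one: 2 × 0.598 × 0.402 = 0.481 (t: 2 × 0.588 × 0.412 = 0.485).
- Both: 0.598² = 0.358.
- Neither: 0.402² = 0.162.

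**4. Uneven splits** (normal approximation, δ = 0.60, one-sided 0.10)

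| Per-arm split | Power, smaller stratum | Power, larger stratum | Exactly one significant |
|---|---|---|---|
| 13 / 13 | 0.598 | 0.598 | 0.481 |
| 10 / 16 | 0.524 | 0.661 | 0.492 |
| 8 / 18 | 0.468 | 0.698 | 0.513 |
| 5 / 21 | 0.370 | 0.746 | 0.564 |

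**5. Other true effects** (equal split, one-sided 0.10)

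| Constant effect (SD) | 0 | 0.2 | 0.4 | 0.5 | 0.6 | 0.8 | 1.0 |
|---|---|---|---|---|---|---|---|
| Exactly one significant | 18% | 34% | 48% | 50% | 48% | 35% | 18% |

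**6. Other cut-offs.** T16 sets no threshold for the stratum p-values. At δ = 0.60 and over the same splits, one-sided 0.05 gives 50–56% and one-sided 0.025 gives 45–50%.

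**7. Given a significant overall result.** In a simulation of 1,000,000 trials with an equal split and δ = 0.60, exactly one stratum was significant in 51.6% of the overall successes. At least one stratum was not significant in 55.8%.

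**8. What the missing contrast would show.** With 13 per arm per stratum, each stratum effect has variance 2/13, so the SE of their difference is √(4/13) = 0.555 SD. That is twice the SE of the overall effect, √(2/26) = 0.277 SD. The 95% CI half-width is 1.96 × 0.555 = 1.09 SD. Power to detect a true between-stratum difference of 0.60 SD at two-sided 0.05 is Φ(0.60/0.555 − 1.96) = 0.19. The difference detectable with 80% power is (1.96 + 0.8416) × 0.555 = 1.55 SD.

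These figures ignore covariate adjustment, multiple imputation and chance imbalance of the arms within strata.

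**The case against.** The strongest reply is that the harm is a possible misreading and not something the plan does. No passage sets a threshold for the stratum p-values or draws a conclusion from comparing them, and the protocol already calls such analyses exploratory. That is correct. A reader might infer that the SAP will declare a severity effect, or a lack of robustness, from discordant p-values; the documents contain no such rule. What stands is that the SAP puts the analysis under a robustness heading and offers no better basis for judging it.

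Second, T16 prints an SE and 95% limits for each stratum. If the strata are fitted separately, the contrast and its SE, √(SE₁² + SE₂²), can be formed by hand. The imprecision is also visible: with 13 per arm each stratum interval is about ±1.96 × √(2/13) = ±0.77 SD. And the two estimates would have opposite signs only about 12% of the time under a constant 0.60 SD effect, so inconsistency here means discordant significance and not reversed effects. All of this stands. It makes the gap small, but the comparison is still left to the reader.

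Some stronger readings are not supported by the documents:
- **Half-size strata.** The severity split is not stated.
- **Copy-reference imputation redone within each stratum from part of the placebo arm.** The SAP does not say whether imputation is repeated by stratum or done once on the FAS.
- **Loss of baseline adjustment.** Baseline AISRS stays in the refitted model. Only the form of any effect modification is coarsened by the cut at 38.
- **Special weight as a key deliverable.** All six outputs in SAP 12.4.2 carry that mark.

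**Conclusion.** The concern holds in a limited form. The plan gives separate severity results with separate one-sided p-values, lists them as sensitivity analyses, and omits the one estimate that bears on severity dependence. At the design effect of 0.60 SD, one stratum would be significant and the other not in about 48% of trials with equal strata, and in 48–56% over the splits tried, even though the effect is the same in both.

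The size depends on the true effect more than on the split. It is close to one half only for effects of about 0.4 to 0.6 SD. So the statement is conditional on the design assumption and is not a general property of the analysis.

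A reader might go further and infer that the primary conclusion is at risk. It is not: the primary test and the gatekept key secondary test do not use the severity analysis. This is a worthwhile correction to a supporting table.

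**What to change.** In SAP 10.7.3.5 and shell T16:

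1. Add the Week 6 treatment-by-severity contrast (severe minus moderate) with its 95% CI. Take it from one FAS model on the main imputed datasets, adding severity group, treatment-by-severity and treatment-by-severity-by-visit terms with the lower-order terms these need. This also settles that imputation is done once on the FAS.
2. Keep the stratum estimates and their CIs.
3. State that consistency is judged on this contrast and not on the stratum p-values.
4. Label the analysis exploratory, in line with protocol 13.6.6, instead of listing it as a sensitivity analysis.

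An interaction of treatment with continuous baseline AISRS could be added as support. It is optional, because linearity is itself an assumption and a model-based effect below or above 38 would need a chosen evaluation point. Removing the stratum p-values is a matter of presentation and is not required once item 3 is in place.

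The cost is a wording change, one model statement and one row in T16, with no new data and no change to conduct. The drawback is that with an equal split the contrast will have a 95% CI of about ±1.1 SD and can exclude only very large differences. The report should say this plainly.

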### **10.7.4 *Other exploratory analyses***

Exploratory factor analysis will be used as a statistical data reduction technique to determine the underlying constructs of the AISRS scale measures. The maximum-likelihood factor analysis with orthogonal transformation will be used for extraction of factors. Principal components analysis (PCA) with varimax rotation will be used to evaluate the factor structure of the AISRS.

As factor analysis requires complete cases, multiple imputation will be used in case of missing data as described in Section 10.7.2.2.

The analysis will be performed overall in two randomized treatment groups as described in Section 9.1 on FAS. The baseline AISRS scores will be used in current analysis.

A table with AISRS items and corresponding factor loadings after varimax rotation in pca will be produced for each factor extracted in the analysis.

Distribution of the eigen values of the PCA will be reflected on Scree plot.

## 10.8 SECONDARY EFFICACY ENDPOINTS

Change from baseline to Week 1 and 6 in AISRS, CGI-S, ASRS, and CAARS-L-SR are analyzed descriptively reporting by visit: n, mean, standard deviation, Q1 (25th percentile), Q3 (75th percentile), minimum, and maximum, and 95% Confidence Interval for the mean and for the median. For the active doses similar statistics will be reported for the difference from placebo.

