13.3 Subject demographics and other baseline characteristics

Summary statistics will be provided by treatment group for demographics and baseline characteristics, including sex, age, weight, height, BMI, systolic blood pressure, diastolic blood

pressure, geographical region, medical history, baseline values for AISRS, CGI-S, ASRS, and CAARS. These summaries will be performed for the FAS.

Continuous variables will be summarized using n, mean, standard deviation (SD), median, Q1 (25th percentile), Q3 (75th percentile), minimum, and maximum. Categorical variables will be summarized using frequency and incidence.

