13.6.5.2 Other secondary and exploratory efficacy endpoints

Change from baseline to Week 1 and 6 in AISRS, CGI-S, ASRS, and CAARS, as well as sleep quality score and duration, will be analyzed descriptively reporting by treatment: n, mean, standard deviation, Q1 (25th percentile), Q3 (75th percentile), minimum, and maximum, and 95% Confidence Interval for the mean and for the median. Similar statistics will be reported for the difference from placebo. The occurrence of 1-point improvement from baseline to Week 1 and 6 in CGI-S will be reported by a frequency table with proportions in each arm and by proportions' difference and ratio with relevant 95% Confidence Intervals.

For the sleep quality score and sleep duration the endpoint will be measured as the change from the mean of the 7 days preceding treatment to the 7 days preceding the relevant visit (Weeks 1 and 6).

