## 10 STATISTICAL ANALYSIS

### 10.1 GENERAL STATISTICAL METHODOLOGY

Unless otherwise specified:

- Parameters will be shown in tables and listings according to the CRF order;
- In summary tables, all subjects will be grouped by treatment group; the 'LSD' treatment group will be displayed in the first column and 'Placebo' in the second; a 'total' column (including the two treatment groups) may be added in some tables as specified in TLF layouts section;
- Continuous numerical variables will be summarized using the following descriptive statistics: n, mean, standard deviation (SD), median,  $Q_1$  (25th percentile),  $Q_3$  (75th percentile), minimum, and maximum;
- Categorical including ordinal variables will be summarized by frequency and incidence;
- All statistical tests (unless explicitly specified) will be carried out at a significant level ( $\alpha$  level) of 0.05, two-tailed 95% Confidence Interval (CI) will be reported.
- Listings include data from scheduled and unscheduled assessments;
- All listing will be ordered by Treatment, Subject ID, visit/date/time (where applicable).

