### 10.8.1 Key Secondary Endpoint

#### 10.8.1.1 *Change from baseline in AISRS at Week 2*

The change from baseline (see Section 8.1.2) to Week 2 in AISRS Score will be analyzed using the same estimand and imputation process as the primary endpoint. The linear mixed effects model analysis of covariance (ANCOVA) with the change from baseline in the AISRS score at Week 2 following randomization as dependent variable, and treatment group, baseline score of AISRS, sex and age as fixed effects will be used in current analysis. The outcome will be considered confirmatory, if in agreement with the primary endpoint outcome and provided that the null hypothesis is rejected for the primary outcome. This gatekeeping function of the primary outcome allows to avoid any adjustment for multiplicity of testing.

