### 10.8.2 Other Secondary Endpoints

#### 10.8.2.1 *Change in CGI-S from baseline to Week 2 and Week 6*

The change from baseline (see Section 11.2) to Week 2 and Week 6 will be summarized descriptively.

The proportion of subjects having improved or having worsened/being stable will be calculated at each post-baseline assessment by treatment group. The proportion difference and the relative risk (LSD over placebo) with 2-sided 95% CIs will be displayed. The proportion of subjects in each category will be calculated at each post-baseline assessment based on the number of subjects with non-missing CGI-S score.

A listing of CGI-S values over time will be provided for the FAS population.

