### **11.2.2 Change from baseline**

Each change from baseline will be defined as difference between the value at each post-baseline assessment and the baseline value:

Change from baseline= value at post-baseline visit-value at Baseline visit.

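### Differences from placebo in CGI-S, ASRS and CAARS-L-SR are planned from raw change scores; a baseline-adjusted difference with 95% CI should be added, for a gain whose size the documents do not fix

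*SAP*

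**What the plan says.** SAP 10.8 sets the general rule: "Change from baseline to Week 1 and 6 in AISRS, CGI-S, ASRS, and CAARS-L-SR are analyzed descriptively reporting by visit". The listed statistics include a 95% CI for the mean and for the median, and the contrast follows: "For the active doses similar statistics will be reported for the difference from placebo". Protocol 13.6.5.2 has the same rule: "Similar statistics will be reported for the difference from placebo". SAP 10.1 sets the interval level: "two-tailed 95% Confidence Interval (CI) will be reported".

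The endpoint-specific sections name no model. For CGI-S, SAP 10.8.2.1 says: "The change from baseline (see Section 11.2) to Week 2 and Week 6 will be summarized descriptively". SAP 10.8.2.2 treats ASRS and CAARS-L-SR in the same way at Weeks 2, 4 and 6. Change is a plain subtraction (SAP 11.2.2): "Change from baseline= value at post-baseline visit-value at Baseline visit".

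Baseline is available. Protocol 13.3 tabulates "baseline values for AISRS, CGI-S, ASRS, and CAARS", and SAP 8.1.2 lists the same scales.

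AISRS is handled differently. The MMRM for Week 6 (SAP 10.7.2.2) includes baseline AISRS, sex and age. So does the Week 2 ANCOVA (SAP 10.8.1.1): "treatment group, baseline score of AISRS, sex and age as fixed effects will be used in current analysis". The SAP gives no reason for adjusting one scale and not the other three.

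Layout T10 serves CGI-S, ASRS and CAARS-L-SR (SAP 12.4.4.2). It has no row for the difference from placebo and no CI.

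**The concern.** Efficacy against placebo measured by change in CGI-S is a stated secondary objective (Protocol 2.2, SAP 7.2). That is a between-arm question. With no test or model planned, the raw difference and its interval are the only between-arm result on mean change for these scales. CGI-S also has a comparison of proportions improved, but that answers a different question.

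A raw change score fixes the slope of follow-up on baseline at 1. When the true slope differs from 1, two things follow. Noise that baseline could explain stays in the estimate. Any chance baseline difference between the arms also passes partly into the estimated effect. Both matter more in a trial of 26 per arm than in a large one.

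**Working it through.** **Inputs.** From the documents: 26 per arm, 1:1 allocation, two-sided 95% CI, change defined as post-baseline minus baseline. Not in the documents, so assumed: r, the baseline-to-follow-up correlation within arm, and k, the follow-up SD divided by the baseline SD.

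**The plan's own figure.** No precision figure is stated for these scales. The only related one is the primary endpoint's 80% power at a standardised effect of 0.60 and one-sided 0.10 (Protocol 13.6.4). It reproduces: 0.60/√(2/26) = 0.60/0.277 = 2.163; 2.163 − 1.282 = 0.882; power = Φ(0.882) = 81.1% (80.6% with the noncentral t).

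**Precision.** Let the baseline SD be s.

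- Variance of the change score: s²(k² + 1 − 2rk).
- Residual variance after adjusting for baseline: s²k²(1 − r²).
- The first minus the second is s²(1 − rk)². In large samples adjustment is therefore never less precise, and it gains nothing when the slope rk equals 1.
- Large-sample ratio of CI widths, adjusted to raw: √[k²(1 − r²)/(k² + 1 − 2rk)]. With k = 1 this is √[(1 + r)/2].
- Small-sample cost of one covariate at 26 per arm: t(49)/t(50) × √(1 + 1/48) = 1.0005 × 1.0104 = 1.011.

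Two examples:

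- k = 1, r = 0.5: √0.75 = 0.866; × 1.011 = 0.875, or 12.5% narrower. Since 1/0.875² = 1.31, this is worth about 31% more subjects.
- k = 1.5, r = 0.5: √(1.6875/1.75) = 0.982; × 1.011 = 0.993, or 0.7% narrower.

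Expected CI width, adjusted for baseline only, relative to raw change:

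| r | k = 1 | k = 1.25 | k = 1.5 |
|---|---|---|---|
| 0.3 | 0.815 | 0.895 | 0.944 |
| 0.5 | 0.875 | 0.955 | 0.993 |
| 0.6 | 0.904 | 0.981 | 1.007 |
| 0.7 | 0.932 | 1.001 | 1.010 |
| 0.8 | 0.959 | 1.011 | 0.987 |
| 0.9 | 0.985 | 0.985 | 0.891 |

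Simulation of 6,000 trials at each of eight (k, r) pairs agreed within 0.001. In single trials the adjusted interval came out wider than the raw one in 2% of cases at k = 1, r = 0.5; 20% at k = 1, r = 0.8; and 50% at k = 1.5, r = 0.5.

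**Adding sex and age.** With three covariates the cost factor is √(1 + 3/46) × t(47)/t(50) = 1.032 × 1.0016 = 1.034 if sex and age are not prognostic. At k = 1, r = 0.5 the ratio becomes 0.866 × 1.034 = 0.895. At k = 1.5, r = 0.5 it becomes 0.982 × 1.034 = 1.015.

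**Chance imbalance.** The standard error of the baseline difference is √(2/26) = 0.28 baseline SD, and about one trial in three has an imbalance at least that large. With k = 1 and r = 0.5 the raw change score carries (1 − 0.5) × 0.28 = 0.14 SD of it into the estimated effect.

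**Number of fits.** CAARS-L-SR: eight scores (Layout T10) × 3 visits = 24. ASRS: 3. CGI-S: 2. Total 29.

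**The case against.** The case for leaving the plan alone has real substance.

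- *The summaries are descriptive.* No test is attached to them, and formal inference is confined to AISRS, which is already adjusted. This stands: nothing confirmatory depends on the point. It does not remove the gain, because the promised difference is still the only result on mean change for a stated objective.
- *The raw difference is unbiased under randomisation, and baseline values are tabulated by arm.* Both are true. A reader might infer that the planned differences are biased or invalid; the documents do not support that. The loss is efficiency, plus imbalance that a reader can see but cannot correct from the table.
- *The gain is unknown.* This stands. Entry requires CGI-S of at least 4 on a 7-point scale and AISRS of at least 26, both at screening. That could compress the baseline SD relative to follow-up (k above 1), which is where the gain shrinks.
- *Copying the AISRS covariates is not free.* This stands too. It costs about 3% of width if sex and age are not prognostic, and SAP 8.9.1 says the CAARS T-scores are already normed for age and sex.
- *A linear model is rough for a 7-category CGI-S.* True, but the planned difference in means already treats the categories as numbers.

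**Conclusion.** The concern holds as a recommended improvement in precision, not as an error. The plan leaves three secondary scales unadjusted while adjusting AISRS, and gives no reason.

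A reader might conclude that adjustment gives clearly narrower intervals at no cost. The documents do not support that. With 26 per arm and equal SDs, the expected gain falls from 18.5% at r = 0.3 to 4.1% at r = 0.8. If the follow-up SD is 1.5 times the baseline SD, the result lies between 1.3% narrower and 1.0% wider for r from 0.5 to 0.8. The downside is small: about 1.1% of width for baseline alone. No further subjects drop out of the analysis, because a change score needs baseline too.

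These sizes assume normal data, a common slope in the two arms and 26 analysed per arm. At 20 per arm the cost of adjustment rises to about 1.5%. Protection from chance imbalance is a benefit whenever the slope differs from 1.

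Separately, and without any assumption, Layout T10 has no place for the contrast that SAP 10.8 promises.

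**What to change.** In SAP 10.8.2.1 and 10.8.2.2, add for each scale (each score, for CAARS-L-SR) and each visit the LS mean difference, MM-120 minus placebo, with two-sided 95% CI. Take it from an ANCOVA of change on treatment and the baseline value of the same scale. Sex and age are optional, and are not needed for the normed CAARS T-scores. State that the result remains descriptive, with no test.

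Keep the raw summaries by arm. Add rows to Layout T10 for the raw and adjusted differences and their CIs; that shell needs editing in any case.

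The cost is a few sentences of SAP text, one table shell and about 29 fits of a model type that the SAP already uses for AISRS at Week 2. No data collection, sample size or decision rule changes.
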